#### Analysis of Secondary Efficacy Endpoint(s)

We will secondarily compare the intervention and control groups in terms of changes in CMD symptom scores, by measuring depressive symptoms with the 9-item Patient Health questionnaire (PHQ-9) and the HADS anxiety questionnaires. Other outcomes of interest, but not primary targets, include birth outcomes (SGA, LBW, and preterm birth), perceived stress (using the Perceived Stress Scale –PSS), pregnancy-related anxiety (using the Pregnancy Experience Scale PES-Brief), maternal functioning (using WHO-DAS), marital relationships (MacArthur Relationship Questionnaire), IPV, women's empowerment, maternal bonding, maternal responsiveness, child growth at 6 weeks postpartum, as well as initiation and exclusivity of breastfeeding (WHO measures). Pregnancy-related symptoms of anxiety (measured with the PES-Brief) will be assessed at baseline and in the 3rd trimester.

For secondary hypotheses, we will estimate the effects of the intervention using birth and follow-up (6 weeks postpartum) measures separately. Primary analyses will be non-parametric tests, however sensitivity analyses will use parametric models such as linear and logistic regression to control for baseline values of the mothers' characteristics (132). Variable transformations (such as square root or log) will be utilized as appropriate to meet the model assumptions. For primary and secondary endpoints, in all regression models the coefficient on the HMHB vs. non-HMHB (control group) indicator variable will be taken as the estimated effect.

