### **Baseline**

Data will be collected on psychosocial factors (social support, quality of marital relationship, empowerment and functional disability, behavioral activation). We will also collect data on other socio-demographic variables including maternal age (years), maternal weight (kg), socio-economic assets (adapted from the Pakistan DHS), (44) marital status (married, single, widowed), education (years of formal education completed), and literacy (literate, semi-literate, not literate) and medically-related variables including gestational age of current pregnancy, number of pregnancies, history of SGA, LBW, PTB, stillbirth, and any complications in previous pregnancies/births. We will also collect data on current medications and current medical status, i.e. gestational diabetes, hypertension, anemia, mid-upper-arm circumference, smoking, substance abuse, and medication use for depression (though we expect these last three to be uncommon). An intimate partner violence (IPV) screening question will be administered so that referrals can be made if any women experience IPV. Women in the biological sub-study will also have their blood drawn (up to 20 mL) by a study clinician or a research assistant trained in phlebotomy. Each participant will be scheduled as close to possible to the same time of day during the morning hours for all four blood draws (as blood is drawn in HFH between 8:00am and 1:00 pm), allowing us to control for diurnal variation in cytokine levels. Blood will be collected in sodium-heparin tubes for immune cell preparation. Blood will be centrifuged within 8 hours of collection by low-density gradient centrifugation via a Z326 High Performance Centrifuge. Plasma will immediately be frozen in cryovials at -80 C in a ThermoScientific Revco RLE Ultra-Low Lab Freezer and will be stored there until it is shipped to Baltimore for analysis at the end of the trial.

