### **At 3rd trimester**

Data will be collected about anxiety related to the pregnancy/delivery itself (PES-brief), perceived stress, fetal outcome (SGA in utero from medical records), social support, quality of marital relationships, functional disability and cost of service utilization and behavioral activation. An intimate partner violence (IPV) screening question will be administered so that referrals can be made if any women experience IPV. Women in the biological substudy will also have a blood draw (using same techniques described above under 'baseline visit').

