#### Follow-up (6 weeks postpartum):

The primary endpoint will be assessed at six weeks postpartum (with flexibility for -1 week and +4 week window if needed because of scheduling reasons). Women returning for their routine 6-week postpartum visit will be asked to undergo a final follow-up assessment conducted by the Assessment Team, who will be masked to the allocation status of trial participants. Women in the biological substudy will also have a blood draw (using same techniques described above under 'baseline visit'). We will also administer the *Ages & Stages Questionnaire, Third Edition (ASQ-3)* to the infants of all participants in the trial to assess infant neurobehavioral functioning.

For the detailed description of the outcomes and time points, see **Table 4** below.

In the chart below, data collection procedures that are specific to the substudy are marked as Os in the chart instead of as Xs.

Table 4: Schedule of study assessment activities

	Screening	Baseline *	2 nd trimester	3 rd trimester**	Birth	6 weeks postpartum **
	Time 1	Time 2	Time 3	Time 4	Time 5	Time 6
Informed Consent	X	X				
Eligibility assessment						
Screening step 1 (age, residence, stage of pregnancy, language)	X					
Screening Step 2 (medical exclusions)	X					
Screening Step 3 (HADS anxiety inclusion)	X					
Screening Step 4 (SCID MDE exclusion)	X					
Assessments						
Socio-demographic questions		X				
PSS-10 (stress)				X		X
PES-Brief (pregnancy anxiety)		X		X		
PHQ-9 (depressive symptoms)						X
HADS (anxiety symptoms)	X	O	O			X
HADS (symptoms of depression)	X	O	O			X
MDE diagnosis (from SCID)	X					X
MSPSS (social support)	X		X			X
MRQ (relationships)	X		X			X
Empowerment	X					X
WHO-DAS (disability)	X		X			X
DHS IPV items (violence)						X
IPV Screening Question		X		X		(in the DHS module)
PAAS (behavioral activation)		X		X		X
Breastfeeding					X	X
Parenting self-efficacy						X
PBQ (bonding)						X
MIRI (maternal responsiveness)						X
MSEQ (maternal self-efficacy)						X
Anthropometry§§						X
Economic Data						
CSRI				X		X
Blood Draw (for biology aims)	O	O	O			O
Ages & Stages Questionnaire, Third Edition (ASQ-3)						O
From medical records						
Fetal outcome: SGA in utero*				X		
Pregnancy conditions:				X		
Birth outcomes: SGA, PTB, LBW					X	
Medications	X			X		X

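### The secondary symptom comparison calls for a change in PHQ-9, but the PHQ-9 is scheduled only once, at six weeks postpartum; the endpoint should be stated as the six-week score

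*Combined protocol and SAP*

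**What the plan says.** The section Analysis of Secondary Efficacy Endpoint(s) opens: "We will secondarily compare the intervention and control groups in terms of changes in CMD symptom scores". For this it names two instruments, the PHQ-9 for depression and the HADS for anxiety. The next paragraph of that section says that effects for secondary hypotheses will be estimated from the birth and the six-week measures separately. Non-parametric tests are primary there, and regression models controlling for mothers' baseline characteristics are sensitivity analyses. In any regression model the coefficient for study arm is the effect estimate.

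Table 4, under Follow-up (6 weeks postpartum), sets the assessment schedule. Its legend explains that "data collection procedures that are specific to the substudy are marked as Os in the chart instead of as Xs". The three rows that matter are "PHQ-9 (depressive symptoms", "HADS (anxiety symptoms" and "HADS (symptoms of depression" (row labels cut before the closing bracket). The PHQ-9 row has one X, at six weeks postpartum. Each HADS row has an X at screening and at six weeks, with substudy-only marks at baseline and in the second trimester.

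The visit narratives do not add a PHQ-9. The Baseline text begins "Data will be collected on psychosocial factors (social support, quality of marital relationship, empowerment and functional disability, behavioral activation" and goes on to socio-demographic and medical items. The third-trimester text begins "Data will be collected about anxiety related to the pregnancy/delivery itself (PES-brief), perceived stress". Neither names the PHQ-9.

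**The concern.** A change score needs two measurements on the same scale, and for the PHQ-9 the schedule provides one. The analyst would have to decide after the event what the depressive-symptom endpoint is: a six-week score, a change in some other instrument, or something improvised across two scales. The plan should settle that choice before unblinding. Depression is half of the combined outcome the trial targets, and the Background expects the anxiety-focused intervention to carry over to it, so its symptom endpoint should have only one reading.

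There is also a smaller loss of precision. Every trial woman has a depression score from before randomisation, the screening HADS depression subscale, but the plan does not name it as a covariate for the PHQ-9 comparison.

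**Working it through.** The plan gives no figure for this comparison, so there is none to reproduce. The check is a count of scheduled assessments.

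**Step 1. Assessments per main-trial woman in Table 4 (X marks only)**

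| Instrument | Screening | Six weeks | Other columns | Total | Change possible? |
|---|---|---|---|---|---|
| PHQ-9 | none | X | none | 1 | No |
| HADS anxiety | X | X | substudy only | 2 | Yes |
| HADS depression | X | X | substudy only | 2 | Yes |

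**Step 2. Could damage to the table explain it?** Some rows look shifted. Social support, marital relationship and disability carry a mark under the second trimester, where the narrative puts them in the third. A shifted mark in the PHQ-9 row would still be one mark, so a shift cannot create a change score.

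**Step 3. Do other sections schedule a PHQ-9?** The screening procedures and the texts for baseline, 24 weeks, third trimester, birth and six weeks do not mention one. The instrument is named only in the secondary analysis section and in Table 4.

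**Step 4. Is there a pre-randomisation depression score?** Yes. Screening Procedures uses the HADS depression subscale, with a score of 8 or more leading to the SCID depression module. This agrees with the screening X in Table 4.

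**Step 5. What would adjustment gain?** Let r be the correlation between screening HADS depression and six-week PHQ-9. Linear adjustment multiplies the residual variance by 1 − r². The documents give no r, so the range 0.3 to 0.5 is an assumption.

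- r = 0.3: 0.3² = 0.09, a 9% reduction. The standard error is multiplied by √0.91 = 0.954, about 5% smaller.
- r = 0.5: 0.5² = 0.25, a 25% reduction. The standard error is multiplied by √0.75 = 0.866, about 13% smaller.

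The sample-size section plans for 420 outcomes per arm (600 × 0.70 after 30% attrition). At that size the gain is equivalent to 420 / 0.91 ≈ 462 or 420 / 0.75 = 560 unadjusted outcomes per arm. Women with a current major depressive episode are excluded, which may narrow the spread of screening scores and put r below this range.

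**Step 6. HADS anxiety.** A change score is the special case of adjustment in which the slope on the screening score is fixed at 1. Adjusting for the screening score estimates that slope instead and uses the same two measurements.

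**The case against.** The best reply is that the same section largely answers the point. Its second paragraph describes effects estimated from the six-week measures, with the arm coefficient as the estimate and baseline characteristics controlled in sensitivity models. One six-week PHQ-9 is enough for that. This stands, and it limits the point to a mis-stated endpoint. It does not withdraw the word for change in the opening sentence, so two readings remain.

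A second reply is that silence in the schedule is weak evidence. The Baseline text also omits the PES-Brief, which the secondary analysis section and Table 4 both place at baseline. Table 4 has no row for a SCID diagnosis of GAD, which is part of the primary outcome. It has no baseline mark for perceived stress, although the Moderator Analysis uses stress measured at baseline. A note to the table also points to a section 8.2.3 for tool descriptions that is not in these documents. A PHQ-9 mark could have been left out in the same way. That cannot be excluded, but nothing in the documents indicates it.

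A third reply is that symptom scores are not among the secondary objectives listed in the Aims, and that full analysis detail is deferred to a statistical analysis plan to be finalised before unblinding. Both are true. The first limits the importance of the point; the second identifies where to settle it.

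Three stronger readings are tempting and are not supported:

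- A reader might infer that the trial has no depressive-symptom endpoint. It has one, the six-week PHQ-9.
- A reader might infer that the whole symptom comparison fails. The HADS anxiety part can be calculated as stated.
- A reader might infer that the plan intends to subtract a HADS score from a PHQ-9 score. No section proposes this.

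**Conclusion.** The inconsistency is real and confined to one endpoint. Under the schedule as written, a PHQ-9 change is unavailable for all 1200 women, while the HADS anxiety change is available. A between-arm comparison of six-week PHQ-9 scores remains possible. Randomisation keeps it unbiased, subject to the attrition that affects every six-week outcome (30% is anticipated). The primary endpoint is not affected.

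The count rests on Table 4 and the visit narratives being complete for the PHQ-9. The precision gain of 9% to 25% rests on an assumed correlation and may be smaller. It measures the benefit of naming the covariate and should not be read as the harm done by the wording. The point should be corrected before unblinding, but it does not threaten the trial's main conclusion.

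**What to change.** In Analysis of Secondary Efficacy Endpoint(s), and in the statistical analysis plan that is to follow:

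1. Define the depressive-symptom endpoint as the six-week PHQ-9 score compared between arms, with the effect estimate adjusted for the screening HADS depression score.
2. Analyse HADS anxiety as the six-week score adjusted for the screening score.
3. Keep the planned non-parametric test alongside these estimates.
4. Name the covariates in advance. Baseline Descriptive Statistics would adjust for variables found to be unequal between arms, a data-dependent rule that may leave these scores out.
5. Do not add HADS depression as a new outcome. The section names only HADS anxiety, and the depression subscale is needed here only as a covariate.

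If the study forms show that a PHQ-9 is in fact taken before randomisation, correct Table 4 and use that score as the covariate.

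The cost is a change of wording with no new assessment. The small downside is that the effect estimate relies on a regression model, where the section currently gives regression only a sensitivity role.

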## JHSPH IRB Research Plan for New Data Collection

*Use this template for new data collection and if you also will analyze secondary data. Answer the questions below and for numbered sections that do not pertain to your study, retain the section numbers and bolded questions, and write "N/A". Please start typing in the gray boxes provided.*

**PI Name:** [name]

**Study Title:** Happy Mother, Healthy Baby (HMHB) – Anxiety-focused early prenatal intervention for prevention of common mental disorders in Pakistan: An individual randomized clinical trial

**IRB No.:** 9177

**PI Version No. / Date:** April 1, 2022

**I. Aims of the Study:** Describe the aims/objectives of the research and/or the project's research questions or hypotheses.

**This IRB application focuses on the randomized clinical trial that will be conducted after the formative phase of our research (formative work approved, IRB#7678).**

In the primary study, we will evaluate the effectiveness of an evidence-informed, anxiety-focused early prenatal prevention intervention on prevalence of Common Mental Disorders (CMDs) in pregnant women at six weeks' postpartum. We hypothesize that randomization of women with subclinical to clinical levels of prenatal anxiety to the intervention arm will result in fewer cases of CMDs (both Generalized Anxiety Disorder (GAD) and Major Depressive Episode (MDE)) at six weeks' postpartum relative to the routine care arm of mothers with similar levels of baseline anxiety who are not receiving the intervention.

**Primary:** The primary objective of the trial is to evaluate the effect of an evidence-informed, anxiety- focused early prenatal prevention intervention in pregnant women, compared with usual care alone, on prevalence of Common Mental Disorders (CMDs) at six weeks' postpartum.

**Secondary:** Secondary objectives include evaluating the impact of the intervention on prevalence of small-for-gestational age (SGA) at birth, preterm birth (PTB) and low birthweight (LBW) as well as the cost-effectiveness of the intervention. We will examine potential mediators of CMDs and whether the effect of the intervention on CMDs and birth outcomes varies by self-reported perceived stress, quality of marital relationship, empowerment, social support, or history of intimate partner violence.

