Pregnancy conditions: medical status in pregnancy (e.g. pre-eclampsia, gestational diabetes)	X			X	X	X
Adverse event review					AT ALL TIMES	

\*Baseline assessment may be the same day or up to two weeks after screening.

Note: Full descriptions of the assessment tools are given in section 8.2.3.

\*\*Assessments will be somewhat flexible; the 6-week postpartum visit can be done a week early and up to three weeks after the 6 week mark (if scheduling issues preclude collecting data exactly at the desired time)

§This screener will be administered in order to be able to refer women with IPV to counseling, since it is considered an adverse event.

§§Anthropometry will be measured either our team or a healthcare provider at the 6 week postpartum visit.

[figure not shown]
2. Describe the number and type of study visits and/or contacts between the study team and the participant, how long they will last, and where/how they will take place.

For the assessments there will be a screening visit at the time of enrollment, visit at baseline (either at the same time if the woman is ready to enrol or within 2 weeks afterwards if she would like more time to think about it), in late pregnancy, at delivery, and at 6 weeks postpartum. See above for assessments that will be done at each visit. We expect baseline and the 6 week postpartum visits to last between 1 to 1.5 hours. We expect the 3rd trimester visit to be shorter, around 45 minutes. We expect the birth visit to only entail 5 minutes of data collection with the women, while the rest will be gathered from medical records.

For women randomized to the intervention, there will be 6 core intervention sessions and up to 2-6 booster sessions (depending on the time of enrolment). The first five core sessions will be delivered weekly as early in the pregnancy as possible, then the booster sessions will occur, with one final core session (Core Session 6) in the 3rd trimester. Booster sessions will be scheduled on a case by case basis, depending on the recruitment time of the pregnant mother. Please see Table 2 above for an outline of session content.

For women in the biological substudy, there will be an additional visit at 24 weeks gestation for a blood draw and HADS administration. See the Figure below for a timeline of study visits.

Figure: Timeline for participants in the intervention and control arms of the main trial

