## Moderator Analysis

To examine potential effect modifiers of the intervention treatment effects on birth outcomes, we will expand the regression models to include a term for the interaction between intervention group status and the potential moderators (exposure to social support, stress levels, marital relationship and empowerment measured at baseline as well as retrospective report of IPV measured at 6 weeks postpartum). This will allow us to examine whether the effects of HMHB differ for mothers (or their children) with varying levels of the potential moderators; analyses will be informed by recommendations in Aiken and West (1991)(140) and Preacher et al. (2006) (141). This aim will be exploratory given limited power for detecting interaction effects.

5. **Answer the following if they are relevant to your study design:**

- If the study has different arms, explain the process for assigning participants (intervention/control, case/control), including the sequence and timing of the assignment.

Study statistician will produce a random sequence of assignments to the study arms. This sequence will be generated using a pseudo random-number generator, and will be constructed using randomly permuted blocks of size 4, 8, 12, and 16. The assignment list will be printed in order, with each step of the sequence separately stored in opaque envelopes and numbered sequentially. When an individual who has been determined as eligible via the screening procedure subsequently provides consent for study participation, the X will pull the next available envelope, opening it, and recording the assignment to intervention or control.

In addition to the participants randomized through the main study, there will be three arms for the biological study. We will choose the first 100 participants each in the intervention and control arms, and will also recruit a group of 100 healthy controls (HADS <8) who will participate only in the biological study.

- If human biospecimens (blood, urine, saliva, etc.) will be collected, provide details about who will collect the specimen, the volume (ml) and frequency of collection, how the specimen will be used, stored, identified, and disposed of when the study is over. If specimens will be collected for use in future research (beyond this study), complete the "Biospecimen Repository" section below.
-

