**Plan to minimize risk (B):** We recognize IPV is an issue that is associated with both anxiety and depression. It has high prevalence rates in urban Pakistan (47). All women will be assessed on a IPV screener at the baseline and 3rd trimester visits as well as the 2013 DHS IPV instrument at the six-week postpartum visit. This will allow us to identify any women needing referrals because of IPV. All women participating in the study regardless of study arm will receive information about where they can seek care for IPV (i.e. the Institute of Psychiatry.) This program, like our prior Thinking Healthy Program (THP) that used CBT to reduce depression, includes several components – related to family engagement, education, problem solving, facilitating women to tap into their support networks– that will help address potential IPV. We have also identified potential interventions based on the WHO's Problem Management+ (PM+) (48, 49) for IPV, which are being reviewed in detail before the start of the trial. Women who report IPV will be referred to the Institute of Psychiatry, Rawalpindi Medical College, where they can receive social services and support for IPV.

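### Intimate partner violence is compared between arms at six weeks using a report with no stated recall period that also serves as violence history; any look-back before enrolment dilutes the effect toward no difference

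*Combined protocol and SAP*

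**What the plan says.** All references are to the combined protocol and SAP.

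- **Outcome role.** Analysis of Secondary Efficacy Endpoint(s) names, among outcomes of interest that are not primary targets, "marital relationships (MacArthur Relationship Questionnaire), IPV, women's empowerment, maternal bonding, maternal responsiveness, child growth at 6 weeks postpartum". Effects are to be estimated "using birth and follow-up (6 weeks postpartum) measures separately". The main tests are non-parametric; regression on baseline characteristics appears only as a sensitivity analysis.
- **Source at six weeks.** Table 4 schedules no IPV measure at birth. At six weeks it lists the DHS IPV items and folds the screening question into that module. Section VII, Plan to minimize risk (B), agrees: the screener is used at baseline and third trimester, "as well as the 2013 DHS IPV instrument at the six-week postpartum visit".
- **History role.** Moderator Analysis uses a "retrospective report of IPV measured at 6 weeks postpartum" as an effect modifier. The secondary aims describe the same modifier in the list "quality of marital relationship, empowerment, social support, or history of intimate partner violence".
- **Baseline measure.** The Baseline section says: "An intimate partner violence (IPV) screening question will be administered so that referrals can be made if any women experience IPV". No section uses the answer to date violence or to adjust the IPV outcome.
- **Recall period.** None is given. A note to Table 4 says "Full descriptions of the assessment tools are given in section 8.2.3", but this document has no section with that number.

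**The concern.** One report is asked to do two jobs with opposite time requirements. A history measure has to look back before enrolment. An outcome of the intervention has to look at time after it. If the window reaches back, a woman whose partner was violent only before enrolment can count as a case at six weeks, and nothing delivered in the trial can change that. Randomisation spreads such women evenly over the arms, so they add a constant to both proportions and shrink the relative difference. If the window covers only time after randomisation, the outcome is clean, but the report no longer measures the history named in the aims and the moderator becomes a post-randomisation variable.

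What is at stake is the reading of a null result. Section VII expects several programme components to help with IPV. A diluted comparison showing no difference could be taken as evidence that they do not.

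**Working it through.** **The plan's own figure.** The documents give no prevalence, effect or power for IPV. Section III.B gives 420 evaluable women per arm, for 30% versus 21% with common mental disorders at 85% power. With two-sided alpha 0.05 (assumed; alpha is stated only for the biological substudy):

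n = [1.960·√(2·0.255·0.745) + 1.036·√(0.30·0.70 + 0.21·0.79)]² / 0.09² = 420 per arm, and 420/0.70 = 600 enrolled.

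This reproduces the plan, so 420 per arm is used below.

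**Step 1: how much of a look-back precedes randomisation.** Inputs: baseline at 10 to 22 weeks' gestation (stated for the substudy blood draw; the upper limit is also the trial's inclusion limit); visit at 6 weeks, allowed from 5 to 10 weeks in the follow-up text (the Table 4 note allows only three weeks late). Assumed: birth at 40 weeks.

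Weeks since randomisation = 40 − gestation at enrolment + weeks postpartum.

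- Enrolled at 10 weeks: 40 − 10 + 6 = 36. Enrolled at 22 weeks: 40 − 22 + 6 = 24.
- Assumed 12-month recall: 52 − 36 = 16 to 52 − 24 = 28 weeks precede randomisation (31% to 54%). Over the whole visit window it is 12 to 29 weeks. With birth at 39 weeks the six-week range is 33% to 56%.
- Assumed recall of this pregnancy: 10 to 22 weeks precede it.
- Recall since enrolment or since birth: none.

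These are shares of calendar time, not of cases.

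**Step 2: dilution.** Let A be the proportion with violence before randomisation but inside the window (equal in both arms), p the proportion with violence after it, and o the share of the latter who also had earlier violence. If any violence in the window counts as a case:

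scored prevalence = A + (1 − o)·p.

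Power = Φ{[d·√420 − 1.960·√(2p̄(1−p̄))] / √[p₁(1−p₁) + p₂(1−p₂)]}, where p₁ and p₂ are the two scored proportions, d their difference and p̄ their mean. All prevalences and overlaps are assumptions. The true reduction after randomisation is set at 30%.

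| After randomisation | A | o | Scored | Scored reduction | Power |
|---|---|---|---|---|---|
| 20% vs 14% | 0 | – | 20.0% vs 14.0% | 30% | 64% |
| 20% vs 14% | 20% | 0.2 | 36.0% vs 31.2% | 13% | 31% |
| 20% vs 14% | 20% | 0.5 | 30.0% vs 27.0% | 10% | 16% |
| 20% vs 14% | 20% | 0.8 | 24.0% vs 22.8% | 5% | 6% |
| 30% vs 21% | 0 | – | 30.0% vs 21.0% | 30% | 85% |
| 30% vs 21% | 10% | 0.10 (independent) | 37.0% vs 28.9% | 22% | 70% |
| 30% vs 21% | 40% | 0.40 (independent) | 58.0% vs 52.6% | 9% | 35% |
| 30% vs 21% | 30% | 0.75 | 37.5% vs 35.25% | 6% | 10% |

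With o = 1 the scored difference is zero. With equal p in both arms the scored proportions are also equal, so the type I error is not affected.

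**The case against.** The strongest objection is that the recall period is simply unknown. A report can be retrospective and still cover only the time since enrolment or birth, in which case nothing is diluted. The wording that suggests a longer look-back comes from the moderator text and the aims, not from the outcome definition, and a module with several items could be scored differently for each use. This stands as far as it goes: a reader might infer that earlier violence is definitely scored as outcome and that a real reduction is hidden, and the documents support neither. They give no recall period, the effect disappears completely only if every woman affected afterwards was also affected before, and a score built on recent or frequency items would be diluted less. But Table 4 offers no other six-week IPV measure, and the plan itself uses that visit's report for history. Either window leaves one of its two uses unserved.

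The document also asks only for a brief analysis plan and defers detail to a statistical analysis plan to be finalised before unblinding, and baseline adjustment is already allowed as a sensitivity analysis. That makes the repair easy; it does not make the present outcome defined.

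Finally, IPV is not a primary target, and with 20% versus 14% even a clean score has only 64% power. Both points are correct. They limit the weight of the finding and are a further reason not to over-read a null result.

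**Conclusion.** The point holds in a limited form. IPV is an outcome whose only six-week source is also used as violence history, with no recall period and no restriction to time after randomisation. To the extent that the report reaches back before enrolment, the IPV effect is diluted toward no difference.

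The direction follows from the structure. The size does not: it depends on the unstated recall period, on prevalence and on how far violence persists in the same women. Under the assumptions tabulated, a true 30% reduction is scored as 5% to 22%, with power between 6% and 70%, against 64% or 85% for the clean score. Under a recall since enrolment the dilution is nil. The randomised comparison is not biased under the null, and the primary endpoint and the 420 per arm are untouched. This is worth correcting as a defect in a secondary outcome and does not threaten the trial's main result.

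**What to change.** 1. Define the IPV outcome as violence since enrolment. At visits still to come, put that time anchor on the DHS items, and state which items count and how they are scored.
2. Make the main IPV comparison one adjusted for the IPV screening answer already collected at baseline, instead of leaving adjustment to a sensitivity analysis. Adjustment helps precision but cannot date the violence, so it does not replace the anchor.
3. For six-week reports already taken without the anchor, state the recall period that was used. Keep them in a baseline-adjusted comparison, either analysed separately or pooled with an indicator for questionnaire version.
4. State in advance that a null result from a look-back that predates enrolment will not be interpreted as evidence of no effect on IPV.

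Cost: a phrase on an existing module and one covariate already in hand. The plan is dated April 2022 and describes a study resuming after COVID-19 disruption, so collection is probably under way and two item versions would then exist. An indicator handles a difference in level between versions, but the pooled effect would still mix diluted and undiluted reports. The anchored score is also less comparable with survey prevalence figures. The referral use of the screening question is unchanged.
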